6.1.3. Day 3 (48 hours (\pm 24 hours) post-insertion)

- Vital signs and weight
- 48-hour (\pm 24 hours) post IUD insertion PK sample collection
- Prior and concurrent medication
- Adverse events
- Subject education including:
 - Concomitant contraception - if there are concerns that the IUD is not properly placed, counsel the subject on the need for additional contraception

6.1.4. Days 8, 15, 22, 29 (\pm 1 day) and 57 (\pm 3 days)

- Vital signs and weight
- PK sample collection (at approximately the same time of day as collection of the Day 3, 48-hr PK collection)
- Pelvic exam to confirm IUD placement/string check
- Transvaginal ultrasound, if clinically indicated to confirm adequate IUD placement
- Prior and concurrent medication
- Adverse events
- Subject education including:

- Concomitant contraception - if there are concerns that the IUD is not properly placed, counsel the subject on the need for additional contraception
- **ParaGard Subjects:** Day 57 (± 3 days)
 - Exit Visit procedures should be completed as described in Section 6.1.6.

6.1.5. Months 6, 12, 18, 24, 30, 36, and 48 (± 30 days)

- Vital signs and weight
- PK sample collection
- Pelvic exam to confirm IUD placement/string check
- Transvaginal ultrasound, if clinically indicated to confirm adequate IUD placement
- Prior and concurrent medication
- Adverse events
- Subject education including:
 - Concomitant contraception - if there are concerns that the IUD is not properly placed, counsel the subject on the need for additional contraception

6.1.6. Month 60 (± 30 days) or Exit Visit

- Vital signs and weight
- Pregnancy test (urine)
- PK sample collection
- Pelvic exam to confirm IUD placement/string check
- Transvaginal ultrasound, if clinically indicated to confirm adequate IUD placement
- VeraCept removal
 - The subject's preferred method of contraception will be provided
 - If the subject elects a non-hormonal method of contraception, a 14-day supply will be provided by the site
 - If the subject elects to use hormonal contraceptive pills, a one-month supply of hormonal contraceptive pills will be provided to the subject by the site for the first 2 weeks following VeraCept removal
 - The subject will also be provided with condoms to take with her as an extra precaution if the subject fails to acquire the contraception noted above
 - Subjects should be reminded to avoid conception within 7 days after VeraCept removal
- **ParaGard Subjects**
 - Subjects may continue ParaGard use per standard clinical care or have the device removed

- If ParaGard is removed, subject's preferred method of contraception will be provided as outlined above
- Prior and concurrent medication
- Adverse events

6.1.7. Early Discontinuation Visit

All subjects who request removal of VeraCept before 5 years or ParaGard before Day 57 should follow the procedures of the Exit Visit as described in Section [6.1.6](#).

6.2. Study Measurements and Assessments

All study measurements and assessments to be conducted in this PK study are described below.

6.2.1. Pharmacokinetic Sample Collection and Processing

Blood samples for pharmacokinetic analysis will be collected twice during Screening at least 24 hours apart, on Day 1 prior to insertion, Day 3, approximately 48 hours after insertion, and on Days 8, 15, 22, 29 and 57 at approximately the same time of day as the prior PK collections. Approximately 3-5 mL of whole blood will be collected for each blood draw. The total volume collected from each subject for all pharmacokinetic samples will be approximately 20 mL.

Blood samples will be collected in containers appropriate for serum collection, such as a “red topped” tube, that does not contain an anticoagulant.

Blood samples will be processed for serum as described in the PK Laboratory Manual. The yield of serum will be subdivided into 2 samples (~1 mL each). One of these samples will be shipped as soon as possible to the analytical lab for analysis of total serum copper and the other will be stored at -20°C at the site until completion of the study (or until directed by Sebela or designee) and then sent to the analytical lab in one group.

6.2.2. Allergic Reaction or Hypersensitivity to Components of VeraCept

If a subject experiences allergy-related symptoms or a hypersensitivity reaction (e.g. urticarial allergic skin reaction, rash) while VeraCept is placed, she should be assessed for a possible allergy to the components of VeraCept (nickel, titanium and copper). A clinician will determine the historical relationship between symptoms and IUD use to inform a determination of causality. As needed, a nickel, titanium, and/or copper patch test will be performed and/or an assessment by a specialist for VeraCept users. If the IUD is determined to be the cause or highly suspected of causing the allergic reaction or hypersensitivity, the IUD should be removed, and the AE(s) must be followed until resolution, the condition stabilizes, 30 days post study drug removal, or the subject dies or is lost to follow up (including withdrawal of consent/assent), whichever occurs first.

7. ADVERSE EVENTS

During the study, the investigator or study site personnel will be responsible for querying and recording adverse events (AEs) and serious adverse events (SAEs), as detailed below. For the sponsor to fulfill safety assessment obligations, the investigator must report all SAEs to the

study sponsor, whether or not they result from study participation, within 24 hours of learning of the event.

7.1. Definition of a Serious Adverse Event

A serious adverse event (SAE) is any adverse event occurring within the timelines specified in the protocol that results in any of the following outcomes:

- Death;
- Life-threatening situation (subject is at immediate risk of death);
- Inpatient hospitalization or prolongation of existing hospitalization;
- Persistent or significant disability/incapacity;
- Congenital anomaly/birth defect in the offspring of a subject who received study drug; or
- Important medical events that may not result in death, be immediately life-threatening, or require hospitalization, may be considered an SAE when, based upon appropriate medical judgment, they may jeopardize the subject and may require medical or surgical intervention to prevent one of the outcomes listed in this definition. Examples of serious adverse events include but are not limited to: intensive treatment in an emergency room, hospitalization for any reason, and extensive treatment at home for an adverse event. An ectopic pregnancy is considered a serious adverse event.

7.2. Definition of an Adverse Event

An adverse event is any untoward medical occurrence in a clinical investigation subject administered an investigational product and which does not necessarily have to have a causal relationship with this treatment. An AE can, therefore, be any unfavorable and unintended sign (that could include a clinically significant abnormal laboratory finding), symptom, or disease temporally associated with the use of a medicinal product, whether or not considered related to the medicinal product.

Any AE (i.e., a new event or an exacerbation of a pre-existing condition) with an onset from the day of informed consent/assent through Study Exit should be recorded as an AE on the eCRF. All AEs must be recorded regardless of the severity or relationship to study drug. It is important that investigators also report all AEs that result in expulsion or removal of the investigational product being studied, whether serious or non-serious.

Pregnancy is an outcome, and not an AE in this study.

7.3. Adverse Events of Specific Interest

Adverse events of particular clinical importance, other than SAEs will be classified as adverse events of specific interest (AESIs). For this study, AESIs refer to reports of pain during insertion, pelvic infection (PID or endometritis), expulsion and uterine perforation. AESIs will be identified and assessed by the Medical Monitor during the ongoing monitoring of safety data during the trial, during DMSB meetings and for the Clinical Study Report. For each AESI, a narrative may be written and included in the Clinical Study Report.

7.4. Causality: Serious Adverse Event and Adverse Event Relationship to Study Treatment

An Investigator who is qualified in medicine must make the determination of relationship to the drug for each AE. The relationship of an AE to the drug should be assessed using the guidelines presented in Table 3. An AE for which there has been no causal relationship reported initially will require follow-up to determine causality. Of the definitions in Table 3, “possibly”, “probably” and “related” to an investigational medical product are considered adverse reactions. “Unlikely” and “not related” do not qualify as a causal relationship.

Table 2: Adverse Event Relationship to Drug

Relationship to Drug	Description
Related	Previously known toxicity of agent; or an event that follows a reasonable temporal sequence from administration of the drug; that follows a known or expected response pattern to the suspected drug; that is confirmed by stopping or reducing the dosage of the drug; and that is not explained by any other reasonable hypothesis
Probably related	
The adverse event:
 
Follows a reasonable temporal sequence from the time of study drug administration; and/orFollows a known response pattern to the study drug; andWas unlikely to have been produced by other factors such as the subject's clinical state, therapeutic intervention, or concomitant therapy
Possibly related	
The adverse event:
 
Follows a reasonable temporal sequence from the time of study drug administration; and/orFollows a known response pattern to the study drug; butCould have been produced by other factors such as the subject's clinical state, therapeutic intervention, or concomitant therapy
Unlikely related	
The adverse event:
 
Does not follow a reasonable temporal sequence from the time of study drug administration; andWas likely produced by other factors such as the subject's clinical state, therapeutic intervention, or concomitant therapy but for which relationship cannot be definitely ruled out
Not related	The adverse event can be determined with certainty to have no relationship to the study drug

7.4.1. Clarification of Adverse Events Related to Study Procedures

Any untoward event that occurs from the time of informed consent/assent, including the study drug placement procedure until completion of placement, or from the beginning of the removal procedure until the completion of removal, will be reported as an AE. The AE should be recorded on the AE eCRF with a causality assessment of “related to study drug placement procedure.” If the AE also meets the criteria for an SAE, an SAE report should be completed and submitted to the sponsor.

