6.1.1. Screening Window (Day -60 through Day 1)

Subjects will be screened within 60 days prior to device insertion, and two blood samples will be collected within 28 days from Day 1, and at least 24 hours apart within this screening period (can be performed on Screening and Day 1 visits prior to IUD insertion). The following procedures will be performed at Screening:

- Assess eligibility including inclusion/exclusion criteria
- Distribution of subject materials
- Informed consent and assent, if applicable, PHI and Bill of Rights forms, where applicable
- Demographics and baseline characteristics
- Medical/surgical, gynecological, and menstrual history
- Vital signs, height and weight
- General physical exam
- Pelvic exam
- Cervical cytology
- Cervical infection tests
 - Screening for cervical infection tests are to be done at screening unless these tests have been previously completed within 3 months of the screening visit and were negative. If a subject tests positive prior to IUD insertion, the subject should be treated prior to IUD placement. The subject may be inserted 7 days post-treatment. A cervical infection retest should be done 3-months post-IUD insertion to assure there is not a case of re-infection.
 - Insertion can occur without receipt of test results if there is no clinical evidence of infection. If, after IUD insertion, the screening cervical infection test results are positive, the subject should be treated.
- Pregnancy test-urine
- Prior and concurrent medication
- Subject education
- Baseline serum copper sample

Two baseline blood samples will be collected within 28 days from Day 1, and at least 24 hours apart within this screening period (can be performed on Screening and Day 1 visits prior to IUD insertion)

6.1.2. Device Insertion, Day 1

Prior to IUD placement, the following evaluations will be completed:

- Assessment of Eligibility
- Vital signs and weight

- Pelvic Exam
- Transvaginal ultrasound (if clinically indicated)
- Pregnancy test (urine)
- Prior and concurrent medications
- Pre-insertion PK sample (final baseline sample)
- Adverse events and assess for any changes to health status
- IUD placement
 - If placement is unsuccessful, a second attempt may be made on the same day or within 1 week following the first attempt. If a second attempt is also unsuccessful, the subject will be discontinued early from the study.

Post IUD placement, the following evaluations will be completed:

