4.1.7.4 Adverse Event Relationship to Study Treatment

The relationship of an AE to the drug will be assigned as one of following relationships: not related, unlikely related, possibly related, probably related, and related.

For analysis purposes, “possibly related,” “probably related,” and “related” to an investigational medical product are considered adverse reactions and will be reported as “Related.”

“unlikely related” and “not related” do not qualify as a causal relationship and will be reported as “unrelated”.

A missing relationship will be imputed as “related”.

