4.1.7.5 Adverse Events Related to Study Procedures

Adverse events that occur during the study device placement procedure or removal procedure will be reported on the AE case report form and will be assigned one of the relationships noted in Section 4.1.7.4 by the study Investigator. Any missing relationships will be imputed as “related to the study device placement procedure”.

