4.11.1 Brief Summary of Adverse Events

The number (%) of subjects reporting any of the following events during the study will be reported in the brief summary of AEs for the Safety population:

- AE
- AE related to study device
- AE related to study device placement/removal procedure
- SAE
- SAE related to study device placement/removal procedure
- AE leading to study device removal
- AE leading to study discontinuation
- AE leading to Death

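### Protocol 7.4.1 presets a placement-procedure causality for every event from consent to completed placement, in conflict with Safety SAP 4.1.7.5, where the investigator assigns it

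*Protocol*

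**What the plan says.** Protocol 7.4.1 is headed as a clarification of events related to study procedures. Its operative sentence covers "Any untoward event that occurs from the time of informed consent/assent, including the study drug placement procedure until completion of placement", and also events from the start to the end of the removal procedure. It continues: "The AE should be recorded on the AE eCRF with a causality assessment of" one fixed entry, relatedness to the placement procedure. No other entry is offered and no relatedness condition is set. If the event is also serious, 7.4.1 asks for an SAE report.

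Protocol 7.4 deals with the drug: "An Investigator who is qualified in medicine must make the determination of relationship to the drug for each AE". Its table has five levels, and the two lowest "do not qualify as a causal relationship".

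Safety SAP 4.1.7.4 lists the same five levels: "not related, unlikely related, possibly related, probably related, and related". Safety SAP 4.1.7.5 then takes events during the placement or removal procedure and says that each "will be assigned one of the relationships noted in Section 4.1.7.4 by the study Investigator". It uses the placement-procedure label only to fill in a missing relationship. Safety SAP section 5, on changes from protocol, does not mention this difference.

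Procedure relationship feeds planned outputs. Safety SAP 4.11.1 has a row for "AE related to study device placement/removal procedure" and a matching SAE row. Section 4.11.2 has TEAE and serious TEAE tables by closest procedure relationship, and 4.11.4 has a separate listing.

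**The concern.** A clarification of procedure-related events should apply to events that the procedure caused, or at least to those occurring during it. The rule in 7.4.1 starts at consent and settles causality by timing. Followed literally, it would have a site code a cold during screening, or a sprained ankle between two insertion attempts, as caused by the placement procedure. An event during removal, up to Month 60, would be attributed to placement as well.

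At stake is the meaning of the procedure-related AE and SAE outputs. The SAP intends them to reflect an investigator's judgement, while the protocol tells sites to enter a preset answer. That answer is also not one of the SAP's five levels, so someone must decide later how to map it.

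**Working it through.** The plan states no figure to reproduce. The check sets the rules side by side and follows an event to the outputs.

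**Inputs**
- Event window and label: Protocol 7.4.1.
- Screening: up to 60 days before insertion (Protocol 6.1.1).
- Gap between attempts: "a second attempt may be made on the same day or within 1 week following the first attempt" (Protocol 6.1.2).
- Treatment-emergent: an event that starts or worsens on or after the first treatment date of device insertion (Safety SAP 4.1.7.1).
- AE summaries: TEAEs only, in the Safety population (4.11), meaning women with a successful placement (4.2.1).
- Planned arm size: 20 (Protocol 3.1).

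**Length of the window before completed placement.** 60 days of screening + 7 days between attempts = up to 67 days per woman. The last 7 days arise only after a failed first attempt.

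**Where a labelled event can go**, for events with complete dates that do not worsen later:

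| Event starts | 7.4.1 label | Treatment-emergent? | Outputs it can reach |
|---|---|---|---|
| Screening, before the date of the first attempt | Placement procedure | No | eCRF, listings, any SAE report |
| Day 1, before placement | Placement procedure | Yes, because the rule works by date | The above, plus procedure-related summaries |
| Between a failed and a successful attempt | Placement procedure | Depends on the reading of first treatment date | Listings only, or summaries too |
| During placement | Placement procedure | Yes | Summaries; the SAP wants a five-level rating |
| During removal | Placement procedure, though the procedure is removal | Yes | Summaries, which pool placement and removal |

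**The between-attempt row.** Safety SAP 4.1.2 defines two reference dates: the first attempt and the successful insertion. Section 4.1.7.1 does not say which one is the first treatment date. If it is the first attempt, events in the gap are TEAEs. If it is the successful insertion, events before that date are not.

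**Incomplete dates.** Safety SAP 4.1.8 can move an event onto the first insertion date. This happens when the start day is missing, the month and year match that insertion, and the stop date is later or missing. A screening event with such a date could become treatment-emergent while carrying the preset label.

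**Size of one event.** 1/20 = 0.05, or 5 percentage points of an arm's procedure-related incidence. The documents give no rate for failed first attempts or for events in these intervals, so the expected number cannot be calculated.

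**The case against.** The strongest defence is that 7.4.1 and 7.4 answer different questions. Protocol 7.4 rates relationship to the drug, and 7.4.1 concerns the procedure. Safety SAP 4.11.1 and 4.11.2 report device and procedure relationship separately. A reader might infer that 7.4.1 overrides the five-level drug assessment, but the documents do not support that: a procedure label need not replace the drug judgement. The eCRF is not among the documents, so whether it has separate fields is unknown. This part of the defence stands.

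A reader might also infer that the whole screening period inflates the procedure-related incidence tables. It does not, because the summaries are limited to TEAEs. Nor does the window mean that every screening SAE must be reported at once: Protocol 7.7 starts immediate reporting at insertion.

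A further tempting inference is that the rule distorts the VeraCept–ParaGard comparison. The rule is the same in both arms, and randomization takes place on the day of the first attempt (Protocol 11.2), so events on earlier days precede allocation. If first attempts failed more often with one device, labels from the gap could accrue unevenly, but the documents give no failure rates. Insertion pain is also summarized as an event of specific interest by preferred term, whatever its causality code.

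Finally, the imputation sentence in Safety SAP 4.1.7.5 stands in a paragraph about procedure-time events and is naturally read that way. The placement label on removal events changes no planned table, since placement and removal are pooled.

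What the defence leaves unanswered is that 7.4.1 fixes procedure causality by timing, while 4.1.7.5 leaves it to the investigator even for events during the procedure itself.

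**Conclusion.** The rule is wrong as written, and the point is minor. Protocol 7.4.1 and Safety SAP 4.1.7.5 give incompatible instructions on who assigns procedure causality and for which events.

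The practical effect is limited to wrong attributions on the eCRF, in listings and on any SAE report, plus a small route into the procedure-related tables. That route consists of Day 1 events before placement and, on one reading, events in a gap of at most a week after a failed first attempt. Incomplete start dates can add a few more. The 5 percentage points per woman assume the planned 20 per arm in the Safety population, and that sites follow 7.4.1 literally. No primary or secondary PK endpoint is touched, safety is descriptive, and no bias between arms is shown.

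**What to change.** - **Protocol 7.4.1:** delete the automatic causality. State that events from consent onward are recorded as AEs, and that the investigator assigns their relationship to the procedure, naming placement or removal, on the scale that Safety SAP 4.1.7.5 uses.
- **Safety SAP 4.1.7.5:** add that imputation of a missing relationship applies only to events occurring during a placement or removal procedure. This makes the natural reading explicit.
- **Data already collected:** before final database lock, query events that carry the placement-procedure label and started before placement, between attempts or during removal, and obtain the investigator's own assessment.

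The cost is one protocol clarification to sites, one SAP sentence and probably a few queries. The documents do not show how many events are affected. No PK analysis needs to be rerun.

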7.5. Serious Adverse Event and Adverse Event Severity

The investigator will assess the severity of the AE using the following general guidelines:

Mild: An AE that is usually transient, requiring no special treatment, and does not interfere with the subject's daily activities.

Moderate: An AE that introduces a low level of inconvenience or concern to the subject and may interfere with daily activities but is usually ameliorated by simple therapeutic measures.

Severe: An AE that interrupts a subject's usually daily activity and typically requires systemic drug therapy or other treatment (a severe AE may not necessarily qualify as an SAE).

Life-threatening: An AE that put the subject at immediate risk of death from the event as it occurred. This does not include an event that might have led to death if it had occurred with greater severity.

Fatal: An AE that was the cause of the subject's death.

